A prospective cohort study on the epidemiological
investigation, diagnosis, and treatment of hepatic
encephalopathy

DATE: 16th May,2026

1. Research Background

Hepatic encephalopathy (HE) is a common and serious complication in the course of chronic liver disease and acute liver failure. It presents with a wide range of neuropsychiatric abnormalities, from subclinical changes (mild cognitive impairment) to obvious disorientation, confusion, and even coma. This not only significantly affects patients' quality of life and survival prognosis but also imposes a heavy burden on healthcare systems.

The incidence of HE is approximately 11.6 cases per 100 person-years. Among patients with cirrhosis, the prevalence of overt HE is 10-14%, increasing to 16-21% in those with decompensated cirrhosis, and 10-50% in patients undergoing transjugular intrahepatic portosystemic shunt (TIPS). The prevalence of minimal hepatic encephalopathy (mHE) ranges from 20% to 80%. China currently lacks national, multicenter epidemiological data on HE; in particular, the prevalence and disease outcomes of covert hepatic encephalopathy (CHE) need to be clarified.

Diagnosis of HE is also a major challenge. There remains a lack of definitive laboratory tests, and diagnosis mainly relies on exclusion. Although ammonia plays a key role in the pathophysiology of HE, studies have shown that blood ammonia cannot accurately identify HE, and there is no difference in lactulose treatment between patients with normal versus elevated ammonia levels. Currently, tools such as the Psychometric Hepatic Encephalopathy Score (PHES) are commonly used clinically, but their ability to predict overt HE (OHE) is limited by multiple factors. According to the West Haven criteria, HE is further classified into CHE and OHE. Research on CHE is relatively scarce, and many issues remain to be explored. First, diagnosing CHE is difficult. No laboratory method can diagnose or exclude it, and the diagnostic efficacy of existing tests for CHE requires further evaluation. Second, test performance is suboptimal; not all existing tests have undergone cross-sectional and longitudinal validation. Moreover, because cognitive ability is highly dependent on education and cultural environment, complex tests involving letter or math skills may show greater variability across different countries and cultures.

In the treatment field, although lactulose and rifaximin have been established as core drugs, many unmet clinical needs remain. Multiple mechanisms, including ammonia toxicity, inflammation, oxidative stress, and neurotransmitter abnormalities, participate in the pathogenesis of HE. A treatment strategy that merely reduces blood ammonia cannot fully control the disease. Patient tolerance to lactulose, optimization of primary and secondary prevention strategies in high-risk populations, and accumulation of clinical evidence for emerging therapies such as fecal microbiota transplantation and cell therapy all require further research.

In summary, given the increasing disease burden of HE, the inadequacy of early diagnostic tools, and the limitations of current treatment strategies, conducting epidemiological surveys of HE in the Chinese population, optimizing diagnostic processes, and exploring precision treatment strategies are of great clinical significance and social value.

2. Research Objectives

2.1 Primary Objective

To conduct an epidemiological survey of hepatic encephalopathy in the Chinese population and further explore its diagnosis and treatment.

2.2 Secondary Objectives

1. To investigate the diagnostic value of a newly developed mini-program for new-onset minimal hepatic encephalopathy and compare its efficacy with other tests; to explore whether long-term use of the new mini-program leads to differences in prognosis between patients who have experienced HE and those who have not; to evaluate patient and family compliance with and satisfaction towards the mini-program, as well as the feasibility of promoting this model in clinical practice; to assess the subsequent economic benefits of the mini-program...

2. To investigate the predictive value of the third lumbar skeletal muscle index (L3-SMI) for the prognosis of sarcopenia/frailty/malnutrition in the cirrhotic population...

3. To further evaluate the quality of life of patients with hepatic encephalopathy...

[etc...]

3. Study Design

This study is a prospective, multicenter cohort study. Cirrhotic patients and healthy individuals who meet the inclusion criteria will be recruited from outpatient clinics and inpatient wards. Baseline assessments will be completed, and relevant baseline data will be collected, including: demographic information, cirrhosis details (etiology, previous complications, prior hospitalizations or infections, medication use, TIPS), cirrhosis comorbidities, laboratory test results, imaging findings, results of various tests for hepatic encephalopathy, nutritional status, quality of life, physical measurements, etc. Grouping will be based on predefined endpoints. Different groups of participants will be followed up at month 1, 3, 6 after baseline, and then once every six months. At each follow-up, similar categories of data as baseline will be recorded. Finally, data will be integrated and analyzed, and validated in an external cohort.

4. Study Population

The study subjects are cirrhotic patients and healthy individuals. Recruitment will be conducted among patients attending hospital outpatient or inpatient departments who agree to follow-up. Enrolled individuals will be followed prospectively for 3 years. Patients are required to return for follow-up visits at 1, 3, and 6 months after their first outpatient visit or discharge, and then every six months thereafter. Follow-up will be conducted in person when patients return for visits.

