4.2 Exclusion Criteria

(1) Age <18 years.

(2) Women planning to become pregnant, already pregnant, or breastfeeding.

(3) Incomplete required data.

(4) Unable to expertly use the WeChat mini-program or unstable internet environment.

(5) Presence of red-green color blindness or other uncorrectable visual impairment.

(6) Cardiac, pulmonary, or renal failure, or unstable vital signs.

(7) Unwilling to participate in the study or unable to sign informed consent.

(8) Any other condition that may interfere with study assessments, increase subject risk, or affect study completion, deemed unsuitable by the investigator.

(9) Participation in another clinical trial within the past 3 months or currently participating in another clinical trial.

5. Study Variables

·Exposure factors: Laboratory indicators, blood ammonia, data derived from the newly developed mini-program, MELD score, presence of other diseases (hypertension, diabetes, cardiovascular disease), variables for nutrition and sarcopenia assessment, medication regimens, etc.

·Outcome indicators: Death/discharge against medical advice, liver transplantation, TIPS, hepatic encephalopathy (OHE/CHE), frailty, sarcopenia, malnutrition, decreased quality of life, etc.

·Predictors:

(1).Demographic characteristics: age, sex, education level, anthropometric data (height, weight), etc.

(2).Past medical history and comorbidities: etiology of cirrhosis (viral hepatitis,

autoimmune, alcoholic, etc.), cirrhosis complications (gastrointestinal bleeding, ascites, splenomegaly, hepatic encephalopathy, etc.), comorbidities (hypertension, diabetes, cardiovascular disease, kidney disease, psychiatric disorders; infections, etc.), whether TIPS has been performed, etc.

(3).Laboratory indicators: complete blood count, liver and kidney function, coagulation, blood ammonia, electrolytes, C-reactive protein, procalcitonin; imaging indicators; frailty/sarcopenia-related indicators: handgrip strength (dominant hand), abdominal circumference, body mass index (BMI), etc.

(4).Scores and scales: Child-Pugh class, MELD score, MELD-Na score, PHES score, quality of life (scale), data from the mini-program, etc.

(5).Lifestyle habits (smoking, alcohol consumption, etc.), nutritional intake (protein, calories, etc.), etc.

(6).Medications at baseline (anti-HE drugs, dosage, frequency; psychiatric drugs; other drugs such as diuretics, etc.), medications used at outpatient visit/discharge and their frequency, etc.

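### No route is stated for learning of events in patients who do not return, and the visit origin and the death outcome item need to be settled

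*Protocol*

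**What the plan says.** **Mode and length of follow-up (Section 4, Study Population).** "Enrolled individuals will be followed prospectively for 3 years". The mode is given in one sentence: "Follow-up will be conducted in person when patients return for visits". The protocol states no contact by telephone or messaging, no report from family, and no record or registry search for people who do not attend.

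**Start of the visit schedule.** Section 3 (Study Design) has: "Different groups of participants will be followed up at month 1, 3, 6 after baseline, and then once every six months". Section 4 has: "Patients are required to return for follow-up visits at 1, 3, and 6 months after their first outpatient visit or discharge". Section 3 also says that participants "will be recruited from outpatient clinics and inpatient wards", so some are in hospital at enrolment.

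**Outcomes (Section 5).** The list opens with: "Outcome indicators: Death/discharge against medical advice, liver transplantation". It goes on to TIPS, OHE and covert encephalopathy, and others. The first item is not defined further.

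**Analysis (Section 7).** Kaplan-Meier curves, the log-rank test and Cox regression with competing risks are named as possible analyses.

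**The concern.** A patient who has died cannot return, and one who is comatose or admitted elsewhere may not. If outcomes are learned only at attended visits, the reason for a missing outcome is often the outcome itself. Kaplan-Meier and Cox methods need dated events and censoring that is unrelated to risk. Censoring at the last attended visit fails that condition when death or OHE caused the absence. No later analysis can recover a vital status that was never collected, so this belongs to study conduct and cannot be left to the analysis plan.

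The other two matters affect the same outcomes. If the schedule starts at discharge, an inpatient who dies after the baseline assessment but before discharge never enters it. If discharge against advice is counted together with death, patients who are alive and still at risk are treated as having reached a terminal event.

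**Working it through.** **1. The plan's own figures.** Section 6 gives 358 to 573 patients with cirrhosis, or 421 to 674 after 15% dropout. With Z = 1.96 and W = 0.1:

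- Diseased: 1.96² × 0.667 × 0.333 / 0.01 = 85.3, rounded up to 86.
- Non-diseased: 1.96² × 0.595 × 0.405 / 0.01 = 92.6, rounded up to 93.
- Prevalence 50%: 86/0.5 + 93/0.5 = 358.
- Prevalence 80%: 86/0.8 + 93/0.2 = 572.5, so 573.
- Dropout: 358/0.85 = 421.2 and 573/0.85 = 674.1.

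These reproduce. They serve diagnostic accuracy, not mortality. They are used here only because the 15% is the one expected loss that the protocol states: 0.15 × 421 = 63 patients, or 0.15 × 674 = 101.

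**2. Missed deaths, illustration only.** The protocol gives no death rate. Assume 3-year mortality r of 10-30% in retained patients and k × r in non-returners, with k from 1 to 2, and assume that no death among non-returners is recorded.

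- Missed deaths = 0.15 × N × k × r. For N = 421 this runs from 63.15 × 0.10 = 6 to 63.15 × 0.60 = 38. For N = 674 it runs from 101.1 × 0.10 = 10 to 101.1 × 0.60 = 61.
- Share of all deaths missed = 0.15k / (0.85 + 0.15k). For k = 1 this is 15%. For k = 2 it is 0.30/1.15 = 26%. The share does not depend on r.

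The effect on the estimated risk depends on how non-returners are handled. Take r = 20%. True risk is 20% (k = 1) or 0.85 × 20% + 0.15 × 40% = 23% (k = 2). Counting non-returners as survivors gives 0.85 × 20% = 17%. Leaving them out gives 20%, which is correct for k = 1 and too low for k = 2.

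**3. Discharge against advice, illustration only.** Let r now be the true death risk in the whole cohort (10-30%), d the proportion discharged against advice (assumed 2-10%) and f the fraction of these who die (assumed 20-90%). If every such discharge counts as a death, the recorded risk is r + d(1 − f).

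- Largest inflation: 0.10 + 0.10 × 0.80 = 0.18, a factor of 1.8.
- Smallest: 0.30 + 0.02 × 0.10 = 0.302, a factor of 1.01.

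This error runs opposite to the one in step 2.

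**4. The two visit origins side by side.** The schedule over 3 years has eight visits: months 1, 3, 6, 12, 18, 24, 30 and 36.

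- *Outpatient enrolled at the first visit:* the Section 3 and Section 4 origins can coincide.
- *Inpatient:* baseline data can be collected before discharge, so the Section 4 dates fall later by the remaining length of stay. If Section 4's date were also used as analysis time zero, deaths between baseline and discharge would have no place, and everyone analysed would have survived that interval by construction.
- *Inpatient who leaves the index admission against advice:* the same event starts the Section 4 schedule and is a listed outcome in Section 5.

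**The case against.** The strongest reply has four parts.

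- **Silence is not a prohibition.** The text does not say that events may be learned only at visits. Unplanned readmissions are to be recorded, long-term use of the mini-program is foreseen, and an accompanying family member with a smartphone is required. This stands in part: the accurate charge is that no vital-status source for non-attenders is stated. None of these items supplies one, and no source is given for the readmission data.
- **Both origin sentences are visit timetables.** Analysis time zero is commonly left to a statistical analysis plan, which is not shown here. This stands. The timetables still contradict each other for inpatients, and that conflict is in the protocol itself.
- **Pooling is inferred from a slash.** Section 5 also writes OHE/CHE for distinct grades. Section 2.2 joins sarcopenia, frailty and malnutrition by slashes, and Section 5 then lists them separately. So a composite is the natural reading but not a stated rule. The item remains undefined.
- **Survival may not be central.** The primary objective is an epidemiological survey, the sample size is for diagnostic accuracy, no outcome is ranked, and the survival analyses are optional. This limits the weight of the point but does not remove the gap for outcomes that the protocol lists.

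A reader might go further and infer that the study counts from discharge instead of baseline. It does not: Section 3 counts from baseline, and the fault is the contradiction. A reader might also infer that survival will be overstated and predictor effects attenuated. That is not established. Missed deaths and discharges counted as deaths push in opposite directions, and attenuation needs loss that differs by predictor, which the documents do not show.

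**Conclusion.** The point holds as one gap in ascertainment and two matters to reconcile. It is not a demonstrated bias.

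- No route is stated to learn of death, OHE, transplant or TIPS in patients who do not return. Such events may be missed, and censoring at the last attended visit would be informative.
- The visit origins in Sections 3 and 4 conflict for inpatients.
- Death and discharge against advice form one undefined item.

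The size cannot be computed from the protocol. The 15-26% of deaths missed rests on the stated 15% dropout, an assumed mortality ratio of 1 to 2 and no capture among non-returners. That ratio is not an upper bound, because death may itself be the reason for not returning. Much larger losses need strong assumptions, however. With 20% overall mortality, missing half of all deaths within a 15% loss would require 10 of every 15 non-returners to have died (67%), against 10/85 = 11.8% in those retained, a ratio of about 5.7. The documents do not support a figure of that kind, or any net direction.

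**What to change.** 1. For each missed scheduled visit, record vital status with date, OHE, transplant and TIPS by phone or WeChat, from the patient or the accompanying family member. Section 4.1 already requires both to own a smartphone and use WeChat. This has to be set up before follow-up starts, because late tracing loses dates and contacts.
2. Reconcile Sections 3 and 4, and use the baseline assessment date as the single time zero for all participants, so that in-hospital events after baseline count.
3. Make all-cause death its own outcome. Record discharge against advice separately, follow these patients remotely, and keep the combined item only as a sensitivity analysis.

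The cost is a short contact form, wording changes in Sections 3, 4 and 5, and a few minutes of existing staff time per missed visit. Sample size is unchanged.

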4.1 Inclusion Criteria

(1) Cirrhotic patients and healthy individuals. Cirrhosis is diagnosed by physicians based on imaging, elastography, biopsy, or clinical symptoms.

(2) The patient and their accompanying family member own a smartphone, can

expertly use WeChat and mini-programs, and have a stable internet connection.

(3) Voluntarily sign informed consent, have good compliance, and fully understand this study.

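### The smartphone, WeChat and comprehension criteria apply to the whole cohort, so baseline HE prevalence is likely understated relative to hospital-attending adults with cirrhosis and does not describe the stated target

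*Protocol*

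**What the plan says.** Protocol 2.1 gives the primary objective: "To conduct an epidemiological survey of hepatic encephalopathy in the Chinese population and further explore its diagnosis and treatment". Section 1 names the gap to be filled: "China currently lacks national, multicenter epidemiological data on HE", with CHE prevalence and outcomes singled out.

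Sections 4.1 and 4.2 contain one list of criteria, with no sub-cohort limit:

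- Inclusion (2): "The patient and their accompanying family member own a smartphone", can "expertly use WeChat and mini-programs, and have a stable internet connection".
- Inclusion (3): "Voluntarily sign informed consent, have good compliance, and fully understand this study".
- Exclusion (4): "Unable to expertly use the WeChat mini-program or unstable internet environment".
- Exclusion (6): "Cardiac, pulmonary, or renal failure, or unstable vital signs".
- Exclusion (7): "Unwilling to participate in the study or unable to sign informed consent".

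Evaluation of the mini-program is secondary objective 1 (Section 2.2), and Section 5 also lists mini-program data among the exposures and predictors. Section 4 recruits from hospital outpatient clinics and wards. Against selection bias, Section 5 offers uniform criteria and consecutive rather than convenience recruitment.

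**The concern.** A prevalence survey needs inclusion to be unrelated to the condition, or related to it in a known way. Section 1 describes HE as running from mild cognitive impairment through disorientation and confusion to coma. Expert use of an app, good compliance and full understanding of a study are abilities that this spectrum erodes. Section 1 also says that cognitive performance depends strongly on education, and Section 5 lists age and education as confounders. Older or less educated patients may plausibly be less likely to meet the smartphone criteria. A patient who attends alone, or whose relative lacks the skill, is also lost.

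At stake is the baseline prevalence of OHE and CHE, the quantity the study exists to supply. Selection bias of this kind does not shrink as the sample grows. If patients who are turned away are not recorded, it cannot be corrected later.

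**Working it through.** **1. The plan's own sample size.** Inputs from Section 6: sensitivity 0.667, specificity 0.595, W = 0.1, HE proportion 50% or 80%, dropout 15%. Z = 1.96 is assumed here, since it is stated only for the healthy-population formula.

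- Diseased: 1.96² × 0.667 × 0.333 / 0.1² = 85.3, rounded up to 86.
- Non-diseased: 1.96² × 0.595 × 0.405 / 0.1² = 92.6, rounded up to 93.
- At 50%: 86/0.5 + 93/0.5 = 358.
- At 80%: 86/0.8 + 93/0.2 = 572.5, rounded to 573.
- With dropout: 358/0.85 = 421.2 and 573/0.85 = 674.1.

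The stated 358-573 and 421-674 reproduce. They are set by the precision of sensitivity and specificity, not of a prevalence.

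**2. Effect of differential enrolment.** Let p be the true prevalence among consecutive hospital attendees with cirrhosis. Let r be the enrolment probability of patients with HE divided by that of patients without. Then

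observed prevalence = p·r / (p·r + 1 − p).

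Any r below 1 lowers the result. The document gives no r, so the values below are assumptions. The values of p come from Section 6 (50% and 80% for HE) and Section 1 (14% and 21%, the upper ends of the OHE ranges in all and in decompensated cirrhosis).

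| True p | r = 0.9 | r = 0.75 | r = 0.5 |
|---|---|---|---|
| HE 50% | 47.4% | 42.9% | 33.3% |
| HE 80% | 78.3% | 75.0% | 66.7% |
| OHE 14% | 12.8% | 10.9% | 7.5% |
| OHE 21% | 19.3% | 16.6% | 11.7% |

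Example: 0.5 × 0.75 / (0.5 × 0.75 + 0.5) = 0.375/0.875 = 42.9%.

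**3. Comparison with sampling error.** At p = 50%, the 95% half-width 1.96·√(0.25/N) is 5.2 points for N = 358 and 4.1 points for N = 573. The bias is 2.6 points at r = 0.9, 7.1 at r = 0.75 and 16.7 at r = 0.5. Setting the bias equal to the half-width gives r = 0.448/0.552 = 0.81 (N = 358) and r = 0.459/0.541 = 0.85 (N = 573). If r lies below about 0.81 to 0.85, the bias exceeds the sampling error; if it lies above, it does not.

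**4. The stated safeguard.** Uniform criteria and consecutive recruitment prevent discretionary selection among eligible patients. They apply the same filter to everyone and so leave r unchanged. The matching and stratification in Section 5 operate on enrolled participants and cannot represent those never enrolled.

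**The case against.** Several counter-arguments have force, and they limit what can be claimed.

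- **Direction against China as a whole.** A reader might infer that the study will understate national HE prevalence. The document does not support that. Recruitment is from hospital clinics and wards, which plausibly enriches for decompensated disease, and Section 1 puts OHE at 16-21% there against 10-14% in cirrhosis overall. That pushes prevalence up while the criteria push it down, so the net direction is unknown. Downward bias is supportable only relative to hospital attendees.
- **Overt HE and consent.** It is tempting to say that a patient with OHE can never qualify, or that only the patient's own consent is allowed. HE is episodic, and Section 4 times follow-up from the first outpatient visit or discharge, so enrolment after recovery is not ruled out. The criteria are silent on a representative, and consent pages are not part of the text available here. Neither absolute statement stands.
- **Follow-up.** New OHE over the three years is still captured among those enrolled. The problem is mainly baseline prevalence. For prognosis it is a question of generalisability; no internal bias in within-cohort comparisons is shown.
- **Purpose of the criteria.** They do not serve secondary objective 1 alone, because mini-program data are a study-wide exposure and predictor. That explains why they were written. It does not make them suitable for a survey.
- **Size.** Every figure for the bias rests on an assumed r. With mild selection the bias is smaller than the sampling error.
- **Left to the SAP.** Denominators and weighting commonly belong there. The eligibility criteria are fixed in this protocol, however, and no analysis plan can restore patients who were neither enrolled nor logged.

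**Conclusion.** The concern holds in a bounded form. The primary objective and the eligibility list do not fit each other: the cohort is filtered on abilities that HE impairs, and the stated safeguards leave the filter in place. Relative to consecutive hospital-attending adults with cirrhosis, baseline HE prevalence is likely understated. This is clearest for OHE. It is plausible for CHE, through cognition, age and education. Good compliance in inclusion (3) and the organ-failure exclusion plausibly act in the same direction.

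The size is not derivable from the document. A true 50% would be observed as anything from 47.4% to 33.3% for assumed enrolment ratios from 0.9 to 0.5. No direction can be claimed against all cirrhosis in China. What can be said is that the plan as written yields a prevalence that does not describe its stated target.

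**What to change.** 1. Apply inclusion (2) and exclusion (4) only to the mini-program analyses. Leave the consent requirement in place for everyone.
2. Keep a log of all consecutively screened patients with cirrhosis: age, sex, education, inpatient or outpatient setting, Child-Pugh class, clinical HE grade and reason not enrolled. Recording this for patients who do not enrol needs ethics approval.
3. Report clinically graded OHE over all screened patients. Report CHE only among those tested, weighted for non-enrolment using the log. Untested patients must not enter the CHE denominator, since their status is unknown. The weighting corrects only for selection through the logged variables.
4. Restate the target as hospital-attending adults with cirrhosis.

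If the criteria stay, restrict the prevalence conclusion to smartphone-using hospital attendees able to consent.

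The cost is an amendment to two criteria and the objective wording, a screening log, and the ethics provision for it. The main downside is that the mini-program analyses then use a subset of the cohort. The stated 421-674, being based on diagnostic accuracy, must be read as applying to that subset, or its precision must be restated.

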(7).Record the number, reasons, and length of stay for unplanned rehospitalizations.

(8).Confounders: Severity of liver function, age, education level, etiology of cirrhosis, medication use, prior history of HE, etc.

·Effect modifiers: Child-Pugh class, age, etiology of cirrhosis, etc.

To control selection bias, clear and unified inclusion/exclusion criteria will be used, and participants will be enrolled through consecutive recruitment rather than convenience sampling. To control information bias, tests will be administered by different personnel at different time points to ensure information isolation; testers will be trained and standardized procedures established. Questionnaires will be administered in a quiet, private environment. For confounding bias, when comparing prognoses between groups with different test results, individual matching or frequency matching for important confounders (e.g., age, liver function) may be performed. Stratified analysis of confounders will be conducted during data analysis.

6. Sample Size Determination

$$n_{\text{患病组}} = \frac{Z_{\alpha/2}^2 \times \text{Sensitivity} \times (1 - \text{Sensitivity})}{W^2}$$

$$n_{\text{非患病组}} = \frac{Z_{\alpha/2}^2 \times \text{Specificity} \times (1 - \text{Specificity})}{W^2}$$

$$N_{\text{总}} = \frac{n_{\text{患病组}}}{\text{患病率}} + \frac{n_{\text{非患病组}}}{1 - \text{患病率}}$$

Referring to the reference "Detection of minimal hepatic encephalopathy in patients with cirrhosis based on the Stroop-CN model (NCRCID-CHESS 2106): a prospective multicenter study." The specificity was 0.595, sensitivity 0.667. The proportion of HE in the cirrhotic population is 50-80%, and W was set at 0.1. At a prevalence of 50%, the sample size was 358; at 80%, the sample size was 573. According to the formula, the sample size is calculated to be 358-573 cases. Assuming a dropout rate of 15%, approximately 421-674 cases are ultimately needed.

For the healthy population, using the formula $n = \left(\frac{Z \times \sigma}{W} \right)^2$, with $Z=1.96$, $W=2$, and standard deviation=10, approximately 98 individuals are needed. This is rounded to 120 for collection, which is a common sample size for establishing normal reference values in clinical diagnostic tests.

7. Statistical Analysis Plan

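### Entry is limited to expert mini-program users with good compliance, so a feasibility conclusion for routine practice drawn from this cohort would probably be too favourable

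*Protocol*

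**What the plan says.** Section 2.2, secondary objective 1, lists several aims for the mini-program besides diagnostic value. One is "to evaluate patient and family compliance with and satisfaction towards the mini-program, as well as the feasibility of promoting this model in clinical practice".

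Three eligibility rules bear on that aim:

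- Section 4.1, inclusion (2): "The patient and their accompanying family member own a smartphone, can" "expertly use WeChat and mini-programs, and have a stable internet connection". The rule covers the patient and the family member alike.
- Section 4.1, inclusion (3): "Voluntarily sign informed consent, have good compliance, and fully understand this study". The protocol gives no definition, threshold or method for judging compliance.
- Section 4.2, exclusion (4): "Unable to expertly use the WeChat mini-program or unstable internet environment".

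On selection bias, Section 5 (Study Variables) states: "To control selection bias, clear and unified inclusion/exclusion criteria will be used, and participants will be enrolled through consecutive recruitment rather than convenience sampling".

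**The concern.** Feasibility in clinical practice is a question about the patients a clinic actually sees, including those who lack a device, the skill or a reliable connection. The eligibility rules remove those patients before anything is measured. The good-compliance criterion may also remove people whom an investigator expects to use the tool irregularly, and each centre may judge this differently.

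At stake is the rollout claim. High use in a cohort chosen for its ability to use the tool could be cited in support of offering it to patients of a kind never studied. Analysis cannot repair this afterwards if those patients were neither enrolled nor counted.

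**Working it through.** **1. Is there a planned figure to reproduce?** Not for this point. The protocol gives no expected compliance rate, no feasibility target and no share of patients expected to meet the digital criteria. Its sample size (Section 6) rests on diagnostic accuracy: "The specificity was 0.595, sensitivity 0.667", with W = 0.1 and z = 1.96.

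- Diseased: 1.96² × 0.667 × 0.333 / 0.01 = 85.3, rounded up to 86.
- Non-diseased: 1.96² × 0.595 × 0.405 / 0.01 = 92.6, rounded up to 93.
- At 50% prevalence: 86/0.5 + 93/0.5 = 358. At 80%: 86/0.8 + 93/0.2 = 572.5, so 573.
- With 15% dropout: 358/0.85 = 421 and 573/0.85 = 674.

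These match the stated figures. They show only that the cohort was sized for the accuracy aim, and they neither support nor weaken the present point.

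**2. The objective against the criteria.**

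| Part of the objective | Criterion acting on it | Consequence |
|---|---|---|
| Feasibility in clinical practice | Inclusion (2), exclusion (4): device, expert skill, internet | Patients least able to use the tool are outside the cohort |
| Compliance of patient and family | Inclusion (3), if read as covering use of the tool | Expected poor compliers may be outside the cohort |
| Compliance of patient and family | Inclusion (2), exclusion (4) | Ability is selected; persistence among able users can still vary |
| Satisfaction | Inclusion (2), exclusion (4) | Describes able users only |

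Exclusion (3), "Incomplete required data", could remove further poor users, depending on when it is applied; the protocol does not say.

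**3. Does consecutive recruitment help?** No. It guards against investigators choosing among eligible patients. Here the criteria themselves do the selecting, so a consecutive series of eligible patients still contains only eligible patients.

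**4. How large could the effect be?** Let e be the share of otherwise eligible patients who pass the digital and compliance criteria, c₁ the rate of sustained use among them, and c₀ the rate among those screened out.

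- Rate in all these patients = e·c₁ + (1 − e)·c₀
- Gap between cohort and all patients = (1 − e)·(c₁ − c₀)

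Every input is an assumption. With c₁ = 80%:

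| e | c₀ = 60%: rate (gap) | c₀ = 0%: rate (gap) |
|---|---|---|
| 50% | 70% (10 points) | 40% (40 points) |
| 70% | 74% (6 points) | 56% (24 points) |
| 90% | 78% (2 points) | 72% (8 points) |

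If c₀ = c₁ the gap is zero. The range of 2 to 40 points shows how strongly the answer depends on two quantities that the protocol neither gives nor arranges to collect.

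**The case against.** The strongest reply has four parts.

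- **The compliance wording is generic.** It sits between signing consent and understanding the study, so it most naturally means adherence to the study and its visits, not to the mini-program. This stands as a reading. It does not remove the point, because inclusion (2) and exclusion (4) select on ability to use the tool without any help from inclusion (3).
- **Ability is not adherence.** Expert users may still stop using the tool during the three-year follow-up, so compliance and satisfaction among them can be estimated. This stands in full. A reader might infer that the cohort is selected on the outcome and that the whole objective is unanswerable. The documents do not support that: only the step from able users to routine practice fails.
- **The accuracy aim needs people who can operate the tool.** This also stands, and it is a reason to keep the digital criteria.
- **A protocol may leave logs and denominators to other documents, and this is one clause of one secondary objective.** The absence of a log is not the finding. The finding is that stated criteria conflict with a stated objective; the log is part of the remedy. The limited scope does bear on how much weight the point deserves.

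A reader might also infer that both the compliance and the feasibility figure will be inflated by a known amount. That does not follow either. The protocol defines no feasibility figure, and setting compliance among eligible users against uptake among everyone approached compares two different quantities. Such a comparison also yields its widest gaps only by assuming no use at all among those excluded.

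**Conclusion.** The point holds for the feasibility conclusion. The cohort can describe compliance and satisfaction among digitally able patients and families, but it cannot by itself support a statement about promoting the model in routine care, and such a statement would probably be too favourable.

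The direction rests on one assumption: that patients screened out for lack of device, skill, connection or expected compliance would use the tool less than those admitted. This is very plausible, but no figure in the protocol shows it. The size is unknown, and the range above is illustration only. The diagnostic-accuracy aim and the sample size are not called into question here. The point affects part of a secondary objective, and it is worth acting on because the remedy is cheap and unlogged screening failures are hard to reconstruct later.

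**What to change.** 1. Delete the good-compliance wording from inclusion (3). Keep inclusion (2) and exclusion (4) for the diagnostic-accuracy aim.
2. Log every consecutive cirrhotic patient screened, with the reason for non-entry, identifying failures of inclusion (2) or exclusion (4).
3. Define feasibility as the share who enrol and keep using the mini-program among screened patients who are otherwise eligible. Count failures of inclusion (2) or exclusion (4) as non-users. Leave out exclusions unrelated to the tool, such as pregnancy, organ failure or participation in another trial. A denominator of everyone approached would count those as failures of the mini-program and bias the figure downward.
4. Decide beforehand how to treat reasons that may or may not concern the tool, such as visual impairment or refusal.
5. Report compliance and satisfaction separately, stated as applying to digitally able users only.

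The cost is a one-line eligibility amendment, a denominator definition and a little logging work. The feasibility figure will be less favourable, and loss to follow-up may rise slightly once the compliance wording is gone.
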